1.2.2. Justification for design

This trial is a multicentre open label pragmatic RCT, randomising at the level of the individual in a 1:1 ratio between AOT and standardised breathlessness advice or standardised breathlessness advice alone. AOT is delivered by cylinders or concentrator, via either face mask or nasal cannulae. As a result of this it would not be possible to conduct this study in a blinded fashion.

1.2.3. Justification for choice of intervention(s)

AOT is defined as oxygen used during physical activity, delivered by cylinders or concentrator, via either face mask or nasal cannulae, at a flow maintaining saturations $>90\%$ on oxygen, during the 6MWT. Current British Thoracic Society (BTS) oxygen guidance suggests that patients who desaturate on walking to $<88\%$ and are able to walk more or experience less dyspnoea with oxygen may benefit from AOT (37). Whilst the evidence on which this guidance was made is low grade and states that it should not be given routinely outside the context of LTOT, the end result has been extrapolation to any patient who desaturates, in part because the accompanying quality standards state that it may be ordered to improve mobility 'after appropriate formal assessment that includes an exercise test' (38). This standard does not specifically say that exercise duration or symptoms must decrease, so it is probable that expansion of AOT provision has occurred in any patient who has had exercise testing, in order to comply with this interpretation of the quality standard. Our trial team and collaborators agreed with this from their clinical practice. Consequently we have defined receipt of AOT as normal NHS care for those patients in the OXYPuF trial population who desaturate on exertion.

The comparator is standardised advice for breathlessness which is the provision of advice on use of appropriate pharmacological agents (e.g. morphine, benzodiazepines) and non-pharmacological interventions (e.g. fan, breathing techniques). A true placebo of medical air would be both expensive, logically difficult to blind (due to legal requirements for colouring of oxygen and air cylinders), and inappropriate in a pragmatic trial design, in which placebo effects on symptoms and activity that are separate from the biological effect of oxygen (i.e. correction of hypoxia) should occur in the group receiving AOT, and would occur in a real life context outside the trial. The advice about relief of breathlessness will be standardised and designed in conjunction with patients, and issued to both groups.

1.2.4. Justification of choice of primary outcome(s)

We have chosen to use both a specific validated breathlessness score (MRC), and relevant subscale of Kings' Brief Interstitial Lung Disease (K-BILD) questionnaire because breathlessness is an important outcome; whilst a subscale within a questionnaire validated in IPF obviously has value, the subscale itself is not a validated item, unlike the MRC. Cough and fatigue will also be specifically assessed, in accordance with the core dataset advised for IPF trials, by way of a visual analogue score (VAS) and relevant subscale in K-BILD. Activity levels were also required by the NIHR brief; we will objectively evaluate this in 20% of patients in both arms using the Actigraph device, validated for use both against calorimetry and in daily life in respiratory patients (45, 46). We felt this necessary as self-reported activity by the International Physical Activity Questionnaire (IPAQ) cannot be certain to relate to actual activity, and patients had concurred with this in pre-application patient and public involvement (PPI). We have chosen 20% (n=52) as this exceeds the median number required in 10 validation studies of the device in older adults (n=36), as reported in a systematic review of appropriate data collection and processing when using an Actigraph (47). We will adhere to guidance developed in this review when considering device placement and data analysis, including measures of activity intensity and duration, not just step count.

2. AIMS AND OBJECTIVES

2.1. Internal pilot objectives

The pilot phase of the trial will last 6 months and afford the opportunity to assess both recruitment rate and conduct a qualitative study to explore the acceptability of the trial intervention.

2.1.1. Recruitment rate objective

The aim is to open 50% of sites by 6 months from study approval by the relevant authorities, and target an overall recruitment rate of 2 patients per site, per month.

2.1.2. Qualitative aims and objectives

To explore social acceptability and practical responses to the intervention by conducting qualitative interviews.

2.2. Main trial objectives

2.2.1. Clinical aims and objectives

To determine whether AOT is clinically and cost effective in patients with idiopathic pulmonary fibrosis (IPF). The clinical objectives are determined as follows:

- Whether HRQoL measured using the K-BILD questionnaire is superior after AOT compared to the standardised breathlessness advice alone at 6 months after using the trial allocation.
- Whether breathlessness, determined by the MRC dyspnoea score, is superior after AOT compared to the standardised breathlessness advice alone at 6 months after using the trial allocation.
- Whether exercise capacity and physical activity, as measured by the 6MWT OR the sit to stand test (according to local protocol), and a self-reported activity questionnaire (IPAQ) respectively is superior after AOT compared to the standardised breathlessness advice alone at 6 months after using the trial allocation.

2.2.2. Economic aims and objectives

To assess the cost effectiveness of AOT compared to standardised breathlessness advice alone at 6 months after using the trial allocation using EQ-5D-5L and scheduled and unscheduled health service use relating to IPF.

2.2.3. Mechanistic aims and objectives

To assess objective physical activity by using accelerometers to compare this against self-reported physical activity (using the IPAQ) in the AOT arm compared to standardised breathlessness advice only at 6 months after using the trial allocation.

Collection of blood to be used as part of future research.

3. TRIAL DESIGN AND SETTING

3.1. Trial design

This study is a pragmatic, multicentre, open-label individually randomised controlled clinical trial, where patients will use AOT in a community setting, comparing AOT to standardised breathlessness advice only. There is an internal pilot phase, a detailed process evaluation and a cost-effectiveness study.

3.2. Trial setting

The study is set in secondary care, enrolling participants from approximately 20 hospital outpatient clinics or community oxygen services with the trial intervention used by patients in their own homes. For the treatment arm, oxygen cylinders will be delivered to the participant's home for use in their day-to-day life, hence whilst initial assessment is in secondary care, treatment is received in the community.

3.3. Sub-studies

3.3.1

Qualitative sub-study

The qualitative sub-study will be conducted during the pilot phase of the trial. To explore social acceptability and practical responses to the intervention (48), we will conduct qualitative interviews with a range of clinical and non-clinical staff, including relevant policy makers and stakeholders (n=20) to understand attitudes to AOT and the overall goal of improving HRQoL symptoms and activity level. We are particularly interested in understanding willingness to randomise patients to no AOT, given that this is usual practice in many centres; areas which emerge could guide adjustments to information given to clinicians/sites to enhance recruitment if this is poor. We do not anticipate insurmountable issues with clinicians' equipoise, given the call for this kind of evidence to be generated in the last IPF National Institute for Clinical Excellence (NICE) guidance. However, if attitudes were negative and recruitment was below our amber progression targets, this would prompt discussion with the NIHR regarding continuation. In addition, we will interview approximately 20 of the invited patients in the OXYPuF trial, using photo-voice methods, with follow-up interviews or arts-based workshops 3-6 months later (N.B. which may not be within the pilot period), splitting the sample equally between AOT and standardised breathlessness advice arms, and ensuring diversity in the sample (age, gender, ethnicity etc. as far as possible).

Further recruitment for the qualitative study may be undertaken via patient groups. The topic guide will be developed drawing on existing literature and theories, in particular experience of breathlessness, social stigma of visible oxygen use and the perception that oxygen is always beneficial, in conjunction with our PPI group and co-applicants. Interviews will be audio recorded and transcribed verbatim, prior to qualitative analysis using the Framework method, as described in our previous work (49), which is a systematic approach well suited to interdisciplinary health research and to working with clinical and lay collaborators. A systematic review of arts based approaches in healthcare (50) has found 23 studies in which arts were used for knowledge generation/production mainly using visual (n=21) approaches. These can integrate well with qualitative data to explore patient experience (51), hence we will use visual arts such as painting and photography to add to our data, in particular how experience changes during the trial for an individual, and between groups. Some members of our PPI group will additionally be actively involved as co-researchers in the analysis stage of the research, through a series of data workshops facilitated by a qualitative methodologist, to help ensure that the patient voice remains central to this part of the work.

3.3.2

Objective physical activity study

This sub-study will be conducted at a limited number of centres, by invitation, and will collect physical activity data via an accelerometer. The aim is to enrol 20% of the cohort (n=52), split equally between the AOT and standardised breathlessness advice only arms. The first 26 participants recruited at the invited centres, in each arm, will be asked if they will wear an accelerometer for 7 days at 2 time points; at baseline and then again towards the end of the 6 month trial follow up period. If any of the first 26 participants in either arm do not wish to take part, the process of approaching participants will continue until 26 in each arm is achieved.

If the participant agrees to take part, the accelerometer will be sent via post (from the trials office) to the participant's home with instructions on how to use the accelerometer. They will be advised to wear the accelerometer at all times (except when in water) for 7 days. It is important to note that participating patients should be told that the accelerometer must be worn for 7 days post randomisation **prior to using the allocated trial intervention** and to then return it to the trials office by recorded delivery post after the 7-day period is completed.

Towards the end of the 6 month trial follow up period, prior to the 7 day period before the final study visit, an accelerometer will be sent via post to the participant. The accelerometer can be either returned via post to the trials office or handed to the research team at their final study visit (6 month follow up). The research team at site can then return the accelerometer via post to the trials office.

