6.5. Blinding

The OXYPuF trial is an open label trial.

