9. TRIAL PROCEDURES

The following should be performed/collected at baseline:

Clinic visit 1 (Baseline):

- Weight & Height
- Medical history
- Smoking status
- Shortness of breath (MRC dyspnoea score)
- Spirometry within the last 6 months
- Blood Gases (if saturations are <90% on air as per usual care)
- Full Blood Count (FBC/CBC) and storage of plasma for translational work
- Gas Transfer Test within the last 6 months
- Lung function tests
- Assessment of desaturation both on and off oxygen via either the 6MWT or 1 minute sit to stand
- Completion of the participant completed booklet

In addition, at the baseline visit, following randomisation, advice on breathlessness should be given to all participants, and for those randomised to the AOT arm, the oxygen prescription should be provided. For those centres taking part in the sub-study, interest by the participant in taking part in the sub-study should be ascertained.

The following should take place at the 3 week telephone follow up:

3 weeks post randomisation for AOT arm only:

- Telephone (3 weeks post randomisation) **Completed by staff at BCTU.**

- *The timescale as to when this telephone call takes place depends on when the participant receives the AOT. Depending on site/demand, this may take 2-3 weeks following referral to the oxygen team following randomisation.*

The following should be performed at 3 months follow up:

Clinic Visit 2 (3 months) *May be conducted via video depending on local policy*

- Review prescription for Study
- Survival Check
- SAE
- Completion of EQ-5D-L
- Healthcare utilisation
- SpO₂ check

The following should be performed/collected at 6 months follow up:

Clinic Visit 3 (6 months)

- Survival Check
- SAE Check
- Clinical review
- Check completion of HRQoL
- Blood Gases (if saturations are <90% on air as per usual care)
- Full Blood Count (FBC/CBC) and storage of plasma for translational work
- Recording of lung function (spirometry and gas transfer) if done as part of usual care
- Check completion of HRQoL
- Healthcare utilisation
- Weight
- Smoking status
- Shortness of breath (MRC dyspnoea score)
- Assessment of desaturation both on and off oxygen via either 6MWT or 1 minute sit to stand

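### Accelerometer participants are invited and replaced by arm after open-label allocation, so the activity comparison is not fully protected by randomisation, and its 'baseline' week is post-randomisation

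*Protocol*

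**What the plan says.** **Size and purpose.** Protocol 3.3.2: "The aim is to enrol 20% of the cohort (n=52), split equally between the AOT and standardised breathlessness advice only arms". Section 2.2.3 sets two uses for the data: to compare objective with self-reported activity (IPAQ), and to do so for AOT against advice only at 6 months. Section 1.2.4 gives the reason for the device: self-report may not reflect actual activity.

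**Invitation.** Section 3.3.2: "The first 26 participants recruited at the invited centres, in each arm, will be asked if they will wear an accelerometer for 7 days" at baseline and again near the end of follow-up. If some decline, "the process of approaching participants will continue until 26 in each arm is achieved".

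**When the question is put.** Section 9 places it in the paragraph on what happens at the baseline visit once randomisation is done. At centres in the sub-study, "interest by the participant in taking part in the sub-study should be ascertained". Section 6.5: "The OXYPuF trial is an open label trial".

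**The first device week.** Section 3.3.2 calls it baseline, but then states that "the accelerometer must be worn for 7 days post randomisation" and before the allocated intervention is used. Section 8.2.2.3 repeats this order. The device is posted to the participant's home after agreement.

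**The advice.** Section 9: "at the baseline visit, following randomisation, advice on breathlessness should be given to all participants". Under 6.3, the AOT arm receives AOT plus the advice and the control arm receives the advice alone.

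**The concern.** A quota that is counted and topped up within each arm can only be run once the allocation is known. In an open-label trial the participant knows it too. Each arm's 26 are then the people willing to wear the device given what they were allocated, and replacing refusers fills the places without undoing that selection.

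The protocol gives reasons why willingness might differ by arm. Section 3.3.1 notes that AOT is usual practice in many centres and that oxygen is perceived as always beneficial. If acceptance relates to activity differently in the two arms, the 6-month contrast includes a selection difference as well as any effect of oxygen. This is the trial's only objective measure of daily activity.

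The first week adds a second, smaller problem. It is called baseline but follows a known allocation, so activity in it may already reflect expectation or disappointment. It also cannot precede the whole allocated intervention, because the advice has been given by then.

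**Working it through.** **1. The plan's own figure.** 0.20 × 260 = 52, or 26 per arm. It reproduces. Section 1.2.4 bases it on the median size of device validation studies (36), not on power for a comparison between arms.

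**2. Order of events, from 3.3.2, 6.3, 8.2.2.3 and 9.**

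| Step | AOT arm | Advice-only arm |
|---|---|---|
| Allocation known | yes | yes |
| Advice given at baseline visit | yes | yes |
| Sub-study interest sought, counted by arm | after allocation | after allocation |
| Device posted, first 7-day wear | after advice, before oxygen | after advice, no oxygen |
| Second 7-day wear, before 6-month visit | on allocation | on allocation |

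The first week has the same position relative to the advice and to oxygen in both arms. What differs between arms in that week is the allocation the participant knows about. The requirement to wear the device before the allocated intervention can be met for oxygen but not for the advice, in either arm.

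**3. Size of a selection bias.** The documents give neither uptake nor the difference between acceptors and decliners, so both are assumed. Let u be uptake in an arm and d the acceptor-minus-decliner difference in activity, in SD. The arm mean is u × acceptors + (1 − u) × decliners, so acceptors exceed the arm mean by (1 − u) × d. The bias in the contrast is the difference of these terms:

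- Same u and same d in both arms: 0.
- u = 60% and 90%, d = 0.3: (0.4 − 0.1) × 0.3 = 0.09 SD.
- u = 60% and 90%, d = 0.5: (0.4 − 0.1) × 0.5 = 0.15 SD.

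The standard error of the contrast at 26 per arm is sqrt(2/26) = 0.28 SD, so 0.09 to 0.15 SD is about a third to a half of one standard error. The two-sided 5% test would then reject a true null about 6% to 8% of the time.

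**4. Sensitivity to the assumptions.** Suppose acceptance depends on a latent normal variable correlated ρ with activity. The shift among acceptors is ρ × φ(c)/u, with c = Φ⁻¹(1 − u).

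- Uptake 80% and 50%, same direction, ρ = 0.2 to 0.5: bias 0.09 to 0.22 SD, type I error 6% to 13%.
- Uptake 80% and 60%, opposite directions, ρ = 0.2 to 0.5: bias 0.20 to 0.50 SD, type I error 11% to 43%.
- Uptake 90% in both arms, opposite directions, ρ = 0.2 to 0.5: bias 0.08 to 0.20 SD. Equal uptake alone is therefore not enough for zero bias.

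**5. Approaches needed.** 26/0.6 = 43 and 26/0.9 = 29, so under unequal uptake the arms would also fill over different calendar periods.

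**6. What the quota buys.** The detectable difference at 80% power and two-sided 5% is (1.96 + 0.84) × sqrt(1/n₁ + 1/n₂). At 26/26 it is 0.78 SD. Without the quota, the arm size among 52 has SD sqrt(52 × 0.25) = 3.6 and a 95% range of 19 to 33 under simple 1:1 randomisation. At 19/33 the detectable difference is 0.81 SD.

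**The case against.** **Scope and purpose.** The sub-study is a mechanistic measure in 20% of participants, sized from validation work. The paired device-versus-IPAQ comparison does not need an unselected contrast between arms. This stands and limits the importance of the point. But 2.2.3 also states an AOT-versus-advice comparison at 6 months, and that is the use at risk.

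**The size is hypothetical.** This also stands. No uptake figure is available, the direction is unknown, and zero is possible. At 0.09 to 0.15 SD the distortion is small beside a detectable difference of 0.78 SD.

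**Agreement might come earlier.** Table 8 (12.2) schedules the Actigraph form at the point of randomisation, and a consent form might carry an optional item. Neither places the request before allocation, and prior consent would not undo an invitation run by arm.

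**Stronger readings that the documents do not support.**

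- A reader might infer that the first week is pre-intervention in the AOT arm and post-intervention in controls. It is not: 6.3 and 9 give the advice to everyone at the same visit, and oxygen has been used in neither arm. Nor does the AOT arm always wait for oxygen. Section 9 says only that delivery may take 2 to 3 weeks.
- A reader might infer that the comparison is not randomised at all. The arms are randomised; what randomisation does not protect is entry to the subset.
- A reader might infer that the sponsor will analyse change from, or adjust for, the first week. Section 15 sets out no accelerometer model, so this is a risk created by the label and not a stated analysis.

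**Conclusion.** The point holds in limited form. Invitation and replacement by arm, after an open allocation, make entry to the accelerometer subset depend on acceptance given a known allocation. The AOT-versus-advice activity comparison at 6 months is therefore not fully protected by randomisation.

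The bias is of unknown size and direction. It is zero if acceptance and its relation to activity are the same in both arms. It is about 0.09 to 0.15 SD if uptake is 60% against 90% and acceptors differ from decliners by 0.3 to 0.5 SD, and larger only if selection is stronger or runs in opposite directions. All of these inputs are assumptions.

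Separately, the week labelled baseline is a post-randomisation measure, after the advice and before oxygen in both arms. The wording that puts it before the allocated intervention cannot be met for the advice.

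The point concerns a mechanistic subset of 52. The K-BILD primary outcome and the sample size of 260 are unaffected. It is a cheap improvement, not a threat to the trial's main conclusion.

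**What to change.** 1. In 3.3.2 and 9, have invited centres seek sub-study agreement at consent, before randomisation. Take consecutive agreeing participants until 52, with no quota or replacement by arm.
2. In 3.3.2 and 8.2.2.3, describe the first device week as an early post-randomisation, pre-oxygen measure. State that it is not to be used as a baseline covariate or for change scores, and that arms are compared on the 6-month week.
3. Report by arm the numbers approached, agreeing and returning usable data, since people may still drop out once they know their allocation.

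**Cost.** One question moves earlier in the baseline visit, and a few sentences change. Arm sizes will vary around 26 (SD about 3.6), which at 19/33 raises the detectable difference from 0.78 to 0.81 SD.

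Completing the first wear week before randomisation would give a true baseline. It would also split a visit that now holds randomisation, advice and the oxygen prescription, and would need another contact. It is therefore an option and not part of the request.

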3.4. Assessment of risk

All clinical trials can be considered to involve an element of risk and in accordance with the Birmingham Clinical Trials Unit (BCTU) standard operating procedures this trial has been risk assessed to clarify any risks relating uniquely to this trial beyond that associated with usual care. A Risk Assessment has been conducted and concluded that this trial corresponds to the following categorisation:

Type A = No higher than the risk of standard medical care

4. ELIGIBILITY

4.1. Inclusion criteria

- Aged 18 or over
- Clinically diagnosed IPF, confirmed by an ILD multi-disciplinary team (MDT) linked to an NHS specialist commissioned IPF service
- Breathlessness with MRC dyspnoea score ≥2
- Willing and able to comply with completion of questionnaires out to 6 months post-randomisation
- Able to complete a 6MWT or 1 minute sit to stand test
- Able to use oxygen safely in the opinion of the local investigator

